### 4.5.1 Per protocol Analysis Population

No per protocol population will be analysed in this study.

## 4.6 Withdrawn Subjects

Patients may withdraw informed consent and discontinue from the study at any time, or for any reason, without prejudice to their future treatment. In addition, a patient must be discontinued from the study if any of the following criteria are met:

- Patient non-compliance with the protocol, as agreed by the investigator and the sponsor
- Patient lost to follow-up
- Termination of the study by the sponsor
- Patient experiences an unacceptable toxicity that precludes them from continuing in the study e.g. patient experiences a ventricular arrhythmia (see study protocol Section 12.2), as agreed by the investigator and the sponsor

- Lack of adequate recovery from a DLT, see Section 9.2.1.2 in study protocol
- Failure of toxicity to adequately resolve, as outlined in Section 12.2 in study protocol
- Female patient becomes pregnant
- Patient experiences clinical disease progression
- Patient and/or investigator decision

AEs resulting in discontinuation will be followed as outlined in study protocol Section 9.3.4.

Patients who discontinue during the DLT assessment period (Part A), for any reason other than a DLT, will be replaced. All other patients who discontinue study treatment will not be replaced.

If a patient discontinues treatment prior to study completion, and for reasons other than progression or non-tolerability, every effort should be made to conduct the Final Study Visit assessments as outlined in Section 11.5 of the protocol. The reason for the patient's withdrawal from the study must be recorded in the eCRF.

#### 4.7 Randomisation

This is a non-randomized study. All patients will receive treatment with orally administered BGB324. All patients enrolled in Part B2 will also receive intravenously administered cytarabine and patients enrolled in Part B3 will receive decitabine in addition to BGB324.

#### 4.8 Blinding

This is an open-label study and consequently there are no blinding procedures in operation.

#### 4.9 Sample Size

Part A of the study follows a conventional algorithm (3+3 patients per dose level) to identify the MTD, escalating on 0/3 or 1/6 patients experiencing a DLT. Under this design, there is a 71% chance of escalation if the true but unknown rate of DLT is 20%, and <50% chance of escalation if the true but unknown rate of DLT is >30%. The operating characteristics of this 3+3 design are outlined in Table 1.

**Table 1: Operating Characteristics of the 3+3 Study Design**

True but Unknown Rate of DLT (%)	Probability of Escalation (%)
20	71
30	49
40	31
50	17
60	8

The total sample size of Part A depends upon whether DLT(s) is experienced at a given dose level (i.e. whether 3 or 6 patients have been treated) and how many dose levels are tested in order to reach the MTD. A minimum of 6-10 patients will be treated at the MTD.

The sample size of up to 14 evaluable patients for Parts B1, B2, B3 and B4 and up to 20 evaluable patients in Part B5 in this study has been calculated on the basis of the following assumptions for a one-sided, within-group test of proportions, comparing an anticipated ORR of >20% against the null hypothesis rate of 5%, with power 80% for a test of size 0.2. This

calculation is based on statistical significance at the 0.2 level, since this will be taken as evidence of a trend worthy of further study. Although this is offered as a formal sample size calculation, it is acknowledged that for this early-stage study the analyses will be exploratory in nature, and that no account has been taken of multiplicity inherent in the assessment of several, presumably non-independent criteria, for ORR.

## 5 Statistical Methodology

### 5.1 Planned Analyses

Disposition analyses will be carried out using the Enrolled Population. Demographic and baseline characteristics analyses will be carried out using the Safety Analysis Set. Safety analyses will be carried out using the Safety Analysis Set. Efficacy analyses will be carried out using the Efficacy Analysis Population.

Summary statistics will be presented for continuous variables, by way of n, mean, standard deviation (SD), median, minimum (Min) and maximum (Max) and by way of group frequencies and percentages for categories of categorical variables. No statistical comparison of dose levels or treatment groups will be performed. Percentages will be calculated using the total patients per dose cohort in the given population unless otherwise noted.

All data from this study will be presented in data listings. All listings will be sorted by dose level or treatment group and patient.

Baseline will be defined as the last assessment prior to study drug administration. Typically this will be Cycle 1 Day 1. Where calculated, absolute change from baseline will be presented using the following formula for each parameter: Value at the visit/timepoint – value at baseline.

Data will be presented by dose/cohort and overall in Part A and by treatment group (AML (B1: BGB324 400/200 mg Single agent; B2: BGB324 400/200 mg + Cytarabine; B3: BGB324 400/200 mg + Decitabine; B5: BGB324 400/200 mg + Cytarabine) and MDS (B4: BGB324 400/200 mg) ) and overall in Part B.

Where appropriate, the data for patients who received the MTD during Part A will be combined with that for patients who received the MTD in Part B for the purpose of data summarisation. A clear distinction will be made in the relevant Tables to differentiate between the cohort who received the MTD during the dose escalation phase of Part A, the MTD cohort from the cohort expansion phase in Part A, and the combined MTD cohort.

Any patient treated with bemcentinib beyond disease progression will be followed for the same safety and efficacy assessments as for all other patients enrolled into the study. The data for patients treated beyond progression will be presented in both a combined output (with all patients) and a separate output (reflecting a new period of analysis with the data collected in this period). All data collected will be included in the study CSR and may be presented at congress/symposia.

For subjects in Part B a new period (treated beyond disease progression) will be created if the date of progression < date of any intake of the bemcentinib, to identify patient treated with bemcentinib beyond disease progression and also the visit cycle where the data are collected beyond the disease progression. The data collected during this period will be identified to be added in this analysis.

For Part B analysis, some outputs such as disposition, demographic and baseline characteristics, cancer history, ORR, AE and ECG(QtCF), the data for cohort B2 and B5 will be summarized together.

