#### 5.8.1.1 Subsets

- Non-serious adverse events will be presented by dose level (part A) or treatment group (parts B), system organ class and preferred term

- Related (BGB324) adverse events will be presented by dose level or treatment group, system organ class and preferred term.
- Related (Cytarabine) adverse events will be presented by system organ class and preferred term. (Part B2 only)
- Related (Decitabine) adverse events will be presented by system organ class and preferred term. (Part B3 only)
- Related (Other Anti-Cancer Medications) adverse events will be presented by dose level or treatment group, system organ class and preferred term.
- Serious adverse events will be presented by dose level or treatment group, system organ class and preferred term
- Related (BGB324) serious adverse events will be presented by dose level or treatment group, system organ class and preferred term.
  - Related (Cytarabine) serious adverse events will be presented by system organ class and preferred term. (Part B2 only)
  - Related (Decitabine) serious adverse events will be presented by system organ class and preferred term. (Part B3 only)
  - Related (Other Anti-Cancer Medications) serious adverse events will be presented by dose level or treatment group, system organ class and preferred term.
  - Serious adverse events will be presented by dose level or treatment group, system organ class, preferred term, and maximum CTCAE grade.
- Adverse events leading to discontinuation will be presented by dose level or treatment group, system organ class and preferred term.
- Adverse events  $\geq$  Grade 3 will be presented by dose level or treatment group, system organ class and preferred term.
  - Related (BGB324) adverse events  $\geq$  Grade 3 will be presented by dose level or treatment group, system organ class and preferred term.
  - Related (Cytarabine) adverse events  $\geq$  Grade 3 will be presented by system organ class and preferred term. (Part B2 only)
  - Related (Decitabine) adverse events  $\geq$  Grade 3 will be presented by system organ class and preferred term. (Part B3 only)
- The most frequent MedDRA preferred terms ( $\geq 10\%$  subjects in the overall safety population restricted to each part) will be presented by dose level or treatment group.
- Separate listings will be produced for DLTs, SAEs, related (all 3 types) AEs, discontinuations due to AEs, and events of  $\geq$  Grade 3 severity.

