### **5.8.4 Eastern Cooperative Oncology Group**

ECOG performance status will be summarized categorically at each scheduled visit with frequencies and percentage.

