### **5.8.5 Electrocardiograms**

The quantitative ECG assessments (PR interval, RR interval, QRS Duration, QT interval, and QTcF interval) will be summarised for actual values and Change from Baseline to each visit/timepoint will be also presented.

ECG overall interpretation (normal, abnormal not clinically significant and abnormal clinically significant) will be presented as a categorical summary by dose cohort and scheduled visit.

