**Coagulation:**

Prothrombin Time (PT), Activated Partial Thromboplastin Time (APTT), International Normalized Ratio (INR), and Quick Test.

Numeric Hematology and Clinical Chemistry parameters will be summarised along with each corresponding Change from Baseline for all scheduled visit by dose level or treatment group. The incidence of laboratory test results outside the normal range will be listed by dose cohort and time point.

The following shift tables from baseline to all the cycles of hematology CTCAE grades will also be displayed by dose level or treatment group:

- All post baseline grades according to all baseline grades
- Number of patients with at least CTCAE Grade 2 according to all baseline grades

Finally, number of patients with at least CTCAE Grade 3 at each visit will be summarized.

Clinically significant treatment-emergent laboratory findings will be summarised as adverse events.

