## 5.12 Missing Values – Missing Visits

Missing, unused and spurious data will be considered missing at random and dealt with as such. There is no intention to implement any procedure for replacing missing data.

In case of missing or partially missing dates for initial diagnosis, the following rules will be applied:

- If initial diagnosis date=../mmm/yyyy (= missing day), then it will be substituted by **01/mmm/yyyy**
- If initial diagnosis date=.../.../yyyy (= missing day and month), then it will be substituted by **01/JAN/yyyy**
- If initial diagnosis date=.../.../.... (= completely missing), then it won't be substituted.

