## 6.2 Conventions

Unless otherwise specified, in summary tables of continuous variables, the minimum and maximum values will be displayed to the same number of decimal places as the raw data, the mean and median will be presented to one extra decimal place compared to the raw data, and the standard deviation will be displayed to two extra decimal places compared to the raw data. Wherever possible data will be decimal aligned.

Unless otherwise specified frequency tabulations will be presented by number and percentage, where the percentage is presented in parenthesis to 1 decimal place.

P-values, if applicable, will be presented to 3 decimal places. If a p-value is less than 0.05 but is greater than or equal to 0.01, then an asterisk (\*) will be added next to this value. If a p-value is less than 0.01 but is greater than or equal to 0.001, then two asterisks (\*\*) will be added next to this value. Finally, if the p-value is less than 0.001 then three asterisks (\*\*\*) will be added next to this value and it will be presented as <0.001. If the rounded result is a value of 1.000, it will be displayed as >0.999. Any date information in the listing will use the *date9.* format, for example, 07MAY2002. In the listing, a unit associated with a variable will be presented only once within parentheses either below or next to that variable in the heading portion. If a parameter has multiple units, each unit will be displayed only once, as applicable.

All tables will have their source listing referenced in a footnote. Listings should be sorted by dose level or treatment group, subject and visit and have the source data received by data

management referenced in a footnote. All tables and listings will be converted into Microsoft Word documents and collated into two complete documents.

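### By default, SAP 5.1 divides by-visit categorical safety percentages by the whole cohort, which scales them down by the fraction of patients still assessed

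*SAP*

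**What the plan says.** SAP 5.1 gives a general rule for percentages: "Percentages will be calculated using the total patients per dose cohort in the given population unless otherwise noted". The same section states that "Safety analyses will be carried out using the Safety Analysis Set", and SAP 4.5.2 defines that set as enrolled patients with at least one dose of bemcentinib. The default denominator for a safety table is therefore everyone treated in the cohort.

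Three parts of the safety section call for categorical summaries by visit:

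- SAP 5.8.4: "ECOG performance status will be summarized categorically at each scheduled visit with frequencies and percentage".
- SAP 5.8.5, on the overall ECG interpretation: it "will be presented as a categorical summary by dose cohort and scheduled visit".
- SAP 5.8.7, after the coagulation list: haematology CTCAE shifts from baseline to all cycles, and then "Finally, number of patients with at least CTCAE Grade 3 at each visit will be summarized".

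None of the three names a denominator. SAP 6.2 adds that "Unless otherwise specified frequency tabulations will be presented by number and percentage", so the counts in 5.8.7 also acquire a percentage unless something else is specified. On missing data, SAP 5.12 says "There is no intention to implement any procedure for replacing missing data", and no row for patients not assessed is described.

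The SAP does name another base where its authors wanted one. In 5.8.1.1 the 10% threshold for frequent adverse-event terms refers to "subjects in the overall safety population restricted to each part".

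**The concern.** Treatment has no fixed length. Under SAP 4.3.2 patients stay on drug while the investigator sees benefit, so they leave at different cycles, and the scheduled ECOG, ECG and laboratory assessments stop with them apart from a final visit. A denominator fixed at the cohort total treats a patient who has left as if assessed and found not to be in the category. A table of abnormal ECGs by cycle then mixes two quantities, the rate among patients seen and the fraction of patients seen, and the reader cannot separate them unless the number assessed is printed.

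Safety and tolerability is the Part B primary objective, and SAP 5.8 plans no formal analysis of it, so descriptive tables carry the result. The ECG table matters in particular because Protocol 12.2.1 anticipates that QTc prolongation could be dose-limiting.

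**Working it through.** The plan states no figure on this point, so there is none to reproduce. The check compares the two denominators.

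**Inputs**
- N, patients treated in the cohort. For illustration 14 (the maximum evaluable in B1 to B4) and 20 (the maximum in B5), from SAP 4.9.
- m, patients with a result at the visit. Assumed, because the documents give no retention rate.
- x, patients in the category at the visit. Assumed to be half of m, so that the rate among those assessed is constant.

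**Formulas**
- Rate among those assessed: r = x/m.
- Percentage under the SAP 5.1 default: x/N = r × m/N.
- Since x cannot exceed m, no category can exceed m/N.
- Each assessed patient falls in one category, so the categories at a visit add up to m/N.

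**Results**

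| N | m | x | Cohort total as base, x/N | Patients assessed as base, x/m | Cap, m/N |
|---|---|---|---|---|---|
| 14 | 14 | 7 | 50.0% | 50.0% | 100.0% |
| 14 | 10 | 5 | 35.7% | 50.0% | 71.4% |
| 14 | 4 | 2 | 14.3% | 50.0% | 28.6% |
| 14 | 2 | 1 | 7.1% | 50.0% | 14.3% |
| 20 | 20 | 10 | 50.0% | 50.0% | 100.0% |
| 20 | 10 | 5 | 25.0% | 50.0% | 50.0% |
| 20 | 4 | 2 | 10.0% | 50.0% | 20.0% |
| 20 | 2 | 1 | 5.0% | 50.0% | 10.0% |

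The relation x/N = r × m/N is exact; only m and x are assumed. The scaling applies equally to favourable categories: a normal ECG or an ECOG score of 0 shrinks by the same factor, so the distortion does not always flatter the drug.

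**Does a rising rate have to look like a fall?** No. Suppose 2 of 14 assessed patients are abnormal at an early visit and 4 of 7 at a later one. The rate among those assessed goes from 2/14 = 14.3% to 4/7 = 57.1%. The SAP default shows 2/14 = 14.3% and then 4/14 = 28.6%. The rise is understated but still visible.

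**The case against.** Several points on the other side have weight.

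- **The rule has an escape clause.** It applies only where nothing else is noted, and the SAP uses other bases in places: the 10% adverse-event threshold in 5.8.1.1 and the compliance formula in 5.6. A reader might infer that every percentage in the report is affected. The documents do not support that.
- **The shells were not available.** SAP 6.5 points to a separate shells file, where denominator footnotes and a count of patients assessed could be set. This stands: what can be shown is what the SAP text prescribes, not what the final tables will print.
- **The laboratory item is the weakest case.** SAP 5.8.7 promises only a number for Grade 3 or higher at each visit. The percentage comes from SAP 6.2, and the same convention prints the count beside it. ECOG is the explicit commitment to a percentage by visit.
- **Other outputs carry much of the safety assessment.** Adverse-event incidence is cumulative, and cohort N is the right base for it. Clinically significant laboratory findings (SAP 5.8.7) and ECG changes (Protocol 13.1.1) are also captured as adverse events. Continuous summaries report n, and all data are listed. No hypothesis test changes.
- **The alternative is not neutral.** A percentage of patients assessed is conditional on remaining on study, and at late visits it may rest on two or three patients. The fixed-N figure has a meaning of its own: the share of treated patients observed with the finding at that visit.

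These points limit the scope and consequence of the concern. They do not supply a denominator for the by-visit tables. The last one also explains why the number assessed must be printed whichever base is chosen.

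**Conclusion.** The concern holds in a limited form. As the SAP text stands, categorical safety percentages by visit take the whole treated cohort as base, which multiplies the rate among assessed patients by m/N. With half the cohort assessed, each such percentage is halved. In the illustration with N = 14, a constant 50% prints as 7.1% when two patients remain. These sizes rest on assumed retention.

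A reader might go further and infer that the percentages must shrink towards zero, or that a worsening rate will be shown as falling. Neither follows. The fixed base imposes a cap of m/N, and a percentage can still rise between visits. The End of Study visit is scheduled for every patient, so it need not show the decline. Nor do the documents show that the overall safety conclusion would change, since cumulative adverse-event incidence and continuous summaries are untouched and the shells may already note another base. What is established is that tables serving the primary objective of Part B are specified in a way that confounds frequency with retention.

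**What to change.** Add one sentence to SAP 5.1: for categorical summaries by visit or timepoint, the denominator is the number of patients in the cohort with a non-missing result at that visit; for shift tables, it is the number with both a baseline and a post-baseline result. Print the number assessed next to the cohort N at each visit. Keep cohort N as the base for adverse-event incidence. Align the shells with a matching footnote; if they already carry one, bring the SAP text into agreement with it.

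The cost is one sentence and a footnote, with no new data. The downside is that late-visit percentages will rest on few patients and describe only those still on study. The printed number assessed makes both visible.

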	
survival even after the final study visit. Follow-up can be conducted by phone or visit, contact with family members or community health care providers (family practitioner, nurse or family liaison/social worker), or public health records (where applicable). Every effort should be made to establish the patient's survival status at 3-monthly intervals, or less.

BEMCENTINIB: FORMULATION/DOSE/ROUTE OF ADMINISTRATION:	
Bemcentinib is presented for oral dosing in capsules each containing 100 mg bemcentinib.
 
Patients will be instructed to take bemcentinib on an empty stomach at a similar time each morning when they wake or more than 2 hours after a light meal, with water. To maintain a fasted state, patients should be told not eat or drink anything other than water for at least 1 hour after taking the drug.
 
Bemcentinib will be administered orally according to a daily dosing schedule during each week of continuous 21-day treatment cycles. During Cycle 1 ONLY the first three doses may comprise of a 'loading' dose.
 
Part A: Dose is ascending per dose cohort. The starting dose of bemcentinib (Cohort 1) will be 200 mg on Cycle 1, Days 1, 2 and 3 (loading dose), followed by a daily maintenance dose of 100 mg. This dose may be escalated as agreed by the SMC to a maximum daily loading dose of 400 mg on Days 1, 2 and 3 followed by a maximum daily maintenance dose of 200 mg.
 
Please refer to Section 9.2.1.1 for more details on dose escalation rules.
 
Part B: Bemcentinib will be administered at the MTD or RP2D in Part B1 and Part B4
 
In Parts B2 and B3 bemcentinib will be administered at a dose identified by the SMC, which may be lower than the bemcentinib dose confirmed in Part A. Depending upon the safety profile of bemcentinib observed in Part A the initial starting dose in combination with cytarabine or decitabine may be reduced by a single dose level (e.g., MTD -1) which will be evaluated in at least 3 subjects before introduction of the MTD or RP2D identified in Part A.
 
The bemcentinib dose in Part B will be 400 mg orally daily for the first 3 days of treatment (loading dose) and 200 mg orally daily thereafter (maintenance dose).

DURATION AND FREQUENCY	
Patients may continue to receive bemcentinib for as long as, in the opinion of the investigator, they continue to derive

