9.2.2. Part B

Following SMC review of all treatment emergent safety and efficacy data from Part A, up to 14 evaluable patients (up to 20 evaluable patients in Part B5) will be recruited into each of up to five cohorts (Parts B1, B2, B3, B4 and B5). Depending upon the safety profile of bemcentinib observed in Part A the initial starting dose in combination with cytarabine (Part B2) or decitabine (Part B3), may be reduced by a single dose level (i.e. MTD -1) which may be evaluated in at least three subjects before introduction of the MTD or RP2D identified in Part A.

Recruitment into Part B5 will be overseen by the Sponsor's study team or designee. The number of recruitment slots for patients with refractory AML, defined as no hematological response to last AML treatment and/or patients who have received 2 or more prior treatments for AML, will be restricted to 1/3 of the sample size (i.e. no more than 6 evaluable patients). The study team will notify investigators when recruitment restrictions are applied.

AML Treatment Status	Pre-Screening Approval Requirement
One prior treatment for AML and NOT refractory	Sponsor approval not required prior to screening
Two or more prior treatments for AML	Sponsor approval mandatory prior to screening
Refractory AML*	Sponsor approval mandatory prior to screening

* Refractory AML is defined as no hematological response to last AML treatment and/or patients who have received 2 or more prior treatments for AML (see Appendix 5 of Protocol BGBC003: Modified International Working Group Response Criteria in Acute Myeloid Leukaemia [Cheson , 2003, Döhner, 2017])

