### 4.2.1 Bemcentinib

In Part A, the starting dose of bemcentinib (Cohort 1) will be 200 mg on Cycle 1, Days 1, 2 and 3 (loading dose), followed by a daily maintenance dose of 100 mg. In Part B depending upon the safety profile of bemcentinib observed in Part A the initial starting dose in combination with cytarabine (Part B2) or decitabine (Part B3) may be reduced by a single dose level (i.e. MTD -1) which will be evaluated in at least three patients in each cohort before the introduction of the MTD identified in Part A. The bemcentinib dose level to be investigated in Parts B2 and B3 will be dependent upon the MTD confirmed in Part A. A dose lower than 100 mg daily is not available.

The bemcentinib dose in Part B5 (combination with low dose cytarabine) will be 400 mg orally daily for the first 3 days of treatment (loading dose) and 200 mg orally daily thereafter (maintenance dose).

Patients receiving Formulation 2 will be instructed to take bemcentinib on an empty stomach at a similar time each morning when they wake, or more than 2 hours after a light meal, with water. To maintain a fasted state patients should be told not eat or drink anything other than water for at least 1 hour after taking the drug.

Patients will record their dosing at home in a dosing diary that will be reviewed regularly by the site staff. Patients will be instructed as to the importance of following the dosing instructions they have been provided with, and for maintaining an accurate and up to date dosing record. Patients will also be instructed to bring their dosing diary and all bemcentinib bottles, including unused and empty bottles, with them to each study visit. The site staff will record the amount of used and unused bemcentinib capsules at selected study visits.

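### The B2 and B3 bemcentinib dose is stated both as fixed at 400/200 mg and as SMC-chosen with a possible lower start; SAP 5.1 labels both cohorts 400/200 mg and has no rule for a patient who started lower

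*SAP*

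**What the plan says.** **Fixed dose.** The part of the protocol synopsis on bemcentinib dosing states: "The bemcentinib dose in Part B will be 400 mg orally daily for the first 3 days of treatment", followed by 200 mg daily. Footnote p of Table 5 (B1 and B4) and of Table 6 (B2, B3 and B5) repeats this.

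**SMC-chosen dose.** The paragraph just before that sentence in the synopsis states: "In Parts B2 and B3 bemcentinib will be administered at a dose identified by the SMC, which may be lower than the bemcentinib dose" (the comparison is with the Part A dose). Protocol 9.2.2 says the starting dose "may be reduced by a single dose level (i.e. MTD -1) which may be evaluated in at least three subjects" before the MTD or RP2D is introduced. Protocol 16.8 makes the SMC responsible for defining the B2 and B3 starting dose. The synopsis also allows B2 to escalate from a lower dose up to the single-agent MTD. SAP 4.1 and 4.2.1 carry the same provision; in 4.2.1 the starting dose "may be reduced by a single dose level (i.e. MTD -1) which will be evaluated in at least three patients in each cohort". Protocol 12.1.1 and SAP 4.2.1 name 400/200 mg for B5 only.

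**Reporting.** SAP 5.1 presents Part B by treatment group, with one group per cohort: "B2: BGB324 400/200 mg + Cytarabine; B3: BGB324 400/200 mg + Decitabine". B5 carries the same 400/200 mg label. SAP 5.1 also says that B2 and B5 will be summarised together for disposition, baseline, cancer history, ORR, adverse events and QTcF. SAP 5.14, which lists departures from the protocol, does not mention the lower start.

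**The concern.** SAP 4.1 and 4.2.1 describe cohorts that may contain two starting doses. SAP 5.1 then defines columns that can hold only one. A patient who began B2 or B3 one level lower would fall in a column headed with a dose that he or she did not start on.

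Part B's primary objective is safety and tolerability, so the adverse event and serious adverse event tables are the main output of these cohorts. ORR is the only endpoint with a formal test. Both would be read as results at 400/200 mg. Pooling B2 with B5, whose dose is fixed, would carry any wrong label into a second set of tables. SAP 5.1 also plans to combine Part A and Part B patients who received the MTD. That step needs the dose each patient received, which a cohort-wide label does not supply.

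**Working it through.** **1. Can both dose rules hold?**

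| Place | B2/B3 dose |
|---|---|
| Synopsis (dosing); Table 6 footnote p | 400 mg for 3 days, then 200 mg |
| Synopsis (Part B design and dosing); protocol 9.2.2 and 16.8 | Set by the SMC; may start at MTD -1 |
| SAP 4.1 (Part B) and 4.2.1 | May start at MTD -1 |
| SAP 5.1 | 400/200 mg only |

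The first and second rows agree only if the SMC chose 400/200 mg from the first patient. No text says that it did. The third and fourth rows put the same conflict inside the SAP.

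**2. What a lower start would mean.** This step assumes that the MTD or RP2D is 400/200 mg; neither document states a Part A result. Protocol Table 3 then has one lower level, 200/100 mg. Over a 21-day first cycle (3 loading days and 18 maintenance days):

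- 400/200 mg: 3 × 400 + 18 × 200 = 4800 mg
- 200/100 mg: 3 × 200 + 18 × 100 = 2400 mg

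On that assumption the label would show twice the dose the patient started on.

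**3. How many patients.** The planned sizes are up to 14 evaluable patients in each of B2 and B3 and up to 20 in B5 (protocol 16.9, SAP 4.9). The plan's figure of 14 reproduces. With at least 2 responders in 14, the exact binomial size at 5% is 1 − 0.95^14 − 14 × 0.05 × 0.95^13 = 0.153. The power at 20% is 1 − 0.8^14 − 14 × 0.2 × 0.8^13 = 0.802. The dose label does not alter that calculation; 14 serves here only as a denominator.

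The number of lower-start patients, k, is an assumption, and they are taken to count among the 14. The text gives only a minimum of three if the option is used; six is an illustrative upper case.

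| k in the cohort | Share of 14 (B2 or B3) | Share of pooled B2 and B5 (14 + 20 = 34) |
|---|---|---|
| 0 | 0% | 0% |
| 3 | 3/14 = 21% | 3/34 = 9% |
| 6 | 6/14 = 43% | 6/34 = 18% |

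**4. Would planned outputs show the true dose?** In part. SAP 5.6 summarises exposure and cumulative dose. The table list includes Part B dose reduction and modification and a Part B table of QTcF by grade and dose. The listings include BGB324 exposure and administration by cycle. None of these changes the column headings or contents of the Part B adverse event, serious adverse event or ORR tables.

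**The case against.** The strongest reply is that no affected patient is shown. The reduction is optional everywhere it appears. Protocol 16.8 reports B3 complete and B2 fully enrolled, in a status dated 17 Mar 2020. The table shells named in SAP 6.5 are dated 06Sep2022. The SMC's choice was therefore already known when the shells were prepared, and the 400/200 mg label may simply record it. B5 takes the dose found safe in B2, and that dose is 400/200 mg, which fits. SAP 4.1 and 4.2.1 may only restate protocol text. A lower start would also be traceable in the listings.

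Most of this stands, and it makes the consequence conditional. It does not remove the gap, because neither document says that no one started lower. The general wording that the safety set is analysed by dose group or combination in Part B (protocol 16.4.1, SAP 4.5.2) does not settle how such a patient is shown.

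Four stronger readings are tempting and are not supported:

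- **That B2 and B3 patients are in fact mislabelled.** Nothing shows that a lower start was used.
- **That toxicity at 400/200 mg is diluted, or that the ORR test loses power.** Either would need a lower-dose toxicity or response rate. The documents give none, so no such figure is offered.
- **That the B5 dose choice is undermined.** B5 was already enrolling at the March 2020 status, so column labels in the later shells cannot have informed it.
- **That the documents disagree on whether a lower start is mandatory.** Protocol 9.2.2 says the lower level "which may be evaluated in at least three subjects before introduction of the MTD or RP2D identified in Part A", while SAP 4.2.1 says "which will be evaluated in at least three patients in each cohort before the introduction of the MTD identified in Part A". Both clauses follow an optional reduction. The difference is only whether the three-patient minimum binds once that option is taken.

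**Conclusion.** The contradiction is certain and stands in current text: the B2/B3 dose is both fixed and SMC-chosen, and SAP 5.1 adopts the fixed version without a rule for the other. The effect on results is conditional. If no B2 or B3 patient started below 400/200 mg, the labels are right and only the wording needs repair. If some did, the adverse event, serious adverse event and ORR columns would mix starting doses under one label. At the stated minimum of three patients, that is 21% of a full 14-patient cohort, or about 9% of pooled B2 and B5. These shares assume full cohorts and that the lower-start patients are among the evaluable ones. The stated sample size is unaffected. The point merits correction because it touches the primary-objective tables and the sponsor should already hold the answer.

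**What to change.** - **Protocol and SAP text.** Reconcile the synopsis, protocol 9.2.2 and 16.8, footnote p of Tables 5 and 6, and SAP 4.1, 4.2.1 and 5.1 into one consistent dose statement for each Part B cohort. This review takes no view on which dose is right.
- **SAP 5.1.** Define the B2 and B3 dose label from the starting dose actually received, and state whether any B2 or B3 patient started below 400/200 mg.
- **If any did.** Show those patients by starting dose beside the cohort total in the adverse event, serious adverse event and ORR tables, and identify them in the pooled B2 and B5 outputs.
- **If none did.** Say so and keep the single column.

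The cost is a few sentences and, only if needed, one extra column per affected table, which may hold few patients. The planned exposure and administration listings already draw on the dosing data, so no new data are required.
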